8.3.2 Reasons for Removal From Study

Reasons for removal of a subject from the study might include:

- decision by sponsor or investigator
- withdrawal of consent from study
- death
- lost to follow-up

9. SAFETY DATA COLLECTION, RECORDING, AND REPORTING

9.1 Definition of Safety Events

9.1.1 Disease-related Events

Disease-related events are events (serious or non-serious) anticipated to occur in the study population due to the underlying disease. Fractures (serious or non-serious) are

anticipated to occur in the study population due to the underlying disease. Such events do not meet the definition of an adverse event unless:

- assessed to be more severe than expected for the subject's condition or
- if the investigator believes there is a causal relationship between the IP(s)/study treatment protocol required therapies and disease worsening.

If one of these criteria are met, the disease-related event must be reported as an adverse event or serious adverse event; otherwise, it will be reported as a disease-related event.

Disease-related events and/or disease-related outcomes that do not qualify as serious adverse events:

- An event which is part of the normal course of disease under study (eg, disease progression in oncology or hospitalization due to disease progression) is to be reported as a Disease Related Event.
- Death due to the disease under study is to be recorded on the Event CRF.

If the outcome of the underlying disease is worse than that which would normally be expected for the subject, or if the investigator believes there is a causal relationship between the IP(s)/study treatment protocol required therapies and disease worsening, this must be reported as an adverse event or serious adverse event.

9.1.2 Adverse Events

An adverse event is defined as any untoward medical occurrence in a clinical trial subject. The event does not necessarily have a causal relationship with study treatment. The investigator is responsible for ensuring that any adverse events observed by the investigator or reported by the subject are recorded in the subject's medical record.

The definition of adverse events includes worsening of a pre-existing medical condition. Worsening indicates that the pre-existing medical condition or underlying disease (eg, diabetes, migraine headaches, gout) has increased in severity, frequency, and/or duration more than would be expected, and/or has an association with a significantly worse outcome than expected. A pre-existing condition that has not worsened more than anticipated (ie, more than usual fluctuation of disease) during the study or involves an intervention such as elective cosmetic surgery or a medical procedure while on study, is not considered an adverse event.

An adverse device effect is any adverse event related to the use of a medical device. Adverse device effects include adverse events resulting from insufficient or inadequate

instructions for use, adverse events resulting from any malfunction of the device, or adverse events resulting from use error or from intentional misuse of the device.

The investigator's clinical judgment is used to determine whether a subject is to be removed from treatment due to an adverse event. In the event a subject, or subject's legally acceptable representative requests to withdraw from protocol-required therapies or the study due to an adverse event, refer to [Section 8.1](#) for additional instructions on the procedures recommended for safe withdrawal from protocol-required therapies or the study.

9.1.3 Serious Adverse Events

A serious adverse event is defined as an adverse event that meets at least 1 of the following serious criteria (unless it meets the definition of a disease-related event as defined in [Section 9.1.1](#)):

- fatal
- life threatening (places the subject at immediate risk of death)
- requires in-patient hospitalization or prolongation of existing hospitalization
- results in persistent or significant disability/incapacity
- congenital anomaly/birth defect
- other medically important serious event

A disease-related event is to be reported as a serious adverse event if:

- the subject's pre-existing condition becomes worse than what the investigator would consider typical for a patient with the same underlying condition, or
- if the investigator believes a causal relationship exists between the investigational medicinal product(s)/protocol-required therapies and the event,
- and the event meets at least 1 of the serious criteria above.

An adverse event would meet the criterion of "requires hospitalization", if the event necessitated an admission to a health care facility (eg, overnight stay).

If an investigator considers an event to be clinically important, but it does not meet any of the serious criteria, the event could be classified as a serious adverse event under the criterion of "other medically important serious event". Examples of such events could include allergic bronchospasm, convulsions, blood dyscrasias, DILI (see [Appendix A](#) for DILI reporting criteria), or events that necessitate an emergency room visit, outpatient surgery, or urgent intervention.

The criteria for grade 4 in the CTCAE grading scale differs from the regulatory criteria for serious adverse events. It is left to the investigator's judgment to report these grade 4 abnormalities as serious adverse events.

9.2 Safety Event Reporting Procedures

9.2.1 Reporting Procedures for Disease Related Events

The investigator is responsible for ensuring that all disease-related events observed by the investigator or reported by the subject that occur after first dose of IP through the EOS visit, ET visit, or 30 days after the last dose of IP (whichever period is longer) are reported using the Event CRF. Additionally, the investigator is required to report a fatal disease-related event on the Event CRF.

Events assessed by the investigator to be related to the IP/study treatment/protocol-required therapies, and determined to be serious, require reporting of the event on the Event CRF.

9.2.2 Adverse Events

9.2.2.1 Reporting Procedures for Adverse Events That do not Meet Serious Criteria

The investigator is responsible for ensuring that all adverse events observed by the investigator or reported by the subject that occur after enrollment through the EOS visit, ET visit, or 30 days after the last dose of IP (whichever period is longer) are reported using the Event CRF.

The investigator must assign the following adverse event attributes:

- Adverse event diagnosis or syndrome(s), if known (if not known, signs or symptoms),
- Dates of onset and resolution (if resolved),
- Severity (or toxicity defined below),
- Assessment of relatedness to IP (romosozumab/placebo and/or the PFS), or other protocol-required therapies/protocol-required procedure or activity, and
- Action taken.

The adverse event grading scale used will be the Common Terminology Criteria for Adverse Events (CTCAE). The grading scale used in this study is described in [Appendix A](#).

The investigator must assess whether the adverse event is possibly related to the IP and/or other protocol-required therapies. This relationship is indicated by a "yes" or "no" response to the question: Is there a reasonable possibility that the event may have been caused by the IP and/or other protocol-required therapies?

The investigator must assess whether the adverse event is possibly related to any study-mandated activity (eg, administration of IP, protocol-required therapies, device[s] and/or procedure including any screening procedure[s]). This relationship is indicated by a “yes” or “no” response to the question: “Is there a reasonable possibility that the event may have been caused by a study activity (eg, administration of IP, protocol-required therapies, device[s]), and/or procedure?”

If the severity of an adverse event worsens from the date of onset to the date of resolution, record a single event for each increased level of severity on the Event CRF.

The investigator is responsible for reviewing laboratory test results and determining whether an abnormal value in an individual study subject represents a clinically significant change from the subject’s baseline values. In general, abnormal laboratory findings without clinical significance (based on the investigator’s judgment) are not to be recorded as adverse events. However, laboratory value changes that require treatment or adjustment in current therapy are considered adverse events. Where applicable, clinical sequelae (not the laboratory abnormality) are to be recorded as the adverse event.

The investigator is expected to follow reported adverse events until stabilization or reversibility.

9.2.2.2 Reporting Procedures for Serious Adverse Events

The investigator is responsible for ensuring that all serious adverse events observed by the investigator or reported by the subject that occur after signing of the informed consent through the EOS visit, ET visit, or 30 days after the last dose of IP (whichever period is longer) are recorded in the subject’s medical record and are submitted to Amgen. All serious adverse events must be submitted to Amgen within 24 hours following the investigator’s knowledge of the event via the Event CRF.

If the electronic data capture (EDC) system is unavailable to the site staff to report the serious adverse event, the information is to be reported to Amgen via an electronic Serious Adverse Event Contingency Report Form within 24 hours of the investigator’s knowledge of the event. See [Appendix B](#) for a sample of the Serious Adverse Event Worksheet/electronic Serious Adverse Event Contingency Report Form. For EDC studies where the first notification of a Serious Adverse Event is reported to Amgen via the eSerious Adverse Event Contingency Report Form, the data must be entered into the EDC system when the system is again available.

The investigator must assess whether the serious adverse event is possibly related to any study-mandated activity or procedure. This relationship is indicated by a “yes” or “no” response to the question: “Is there a reasonable possibility that the event may have been caused by a study activity/procedure?”

The investigator is expected to follow reported serious adverse events until stabilization or reversibility.

In addition to the attributes listed in [Section 9.2.2.1](#), the investigator must also complete the serious adverse event section of the Event CRF.

New information relating to a previously reported serious adverse event must be submitted to Amgen. All new information for serious adverse events must be sent to Amgen within 24 hours following knowledge of the new information. The investigator may be asked to provide additional follow up information, which may include a discharge summary or extracts from the medical record. Information provided about the serious adverse event must be consistent with that recorded on the Event CRF.

If a subject is permanently withdrawn from protocol-required therapies because of a serious adverse event, this information must be submitted to Amgen.

To comply with worldwide reporting regulations for serious adverse events, the treatment assignment of subjects who develop serious, unexpected, and related adverse events may be unblinded by Amgen before submission to regulatory authorities. Investigators will receive notification of related serious adverse events reports sent to regulatory authorities in accordance with local requirements.

Amgen will report serious adverse events and/or suspected unexpected serious adverse reactions as required to regulatory authorities, investigators/institutions, and IRBs/IECs in compliance with all reporting requirements according to local regulations and GCP.

The investigator is to notify the appropriate IRB/IEC of serious adverse events occurring at the site and other adverse event reports received from Amgen, in accordance with local procedures and statutes.

9.2.2.3 Reporting Serious Adverse Events After the Protocol-required Reporting Period

There is no requirement to monitor study subjects for serious adverse events following the protocol-required reporting period or after EOS. However, these serious adverse events can be reported to Amgen. If serious adverse events are reported, the

investigator is to report them to Amgen within 24 hours following the investigator's knowledge of the event.

Serious adverse events reported outside of the protocol-required reporting period will be captured within the safety database as clinical trial cases for the purposes of expedited reporting.

9.3 Pregnancy and Lactation Reporting

If a pregnancy occurs in a subject, while the subject is taking protocol-required therapies, report the pregnancy to Amgen as specified below.

In addition to reporting any pregnancies occurring during the study, investigators should monitor for pregnancies that occur after the last dose of protocol-required therapies through 3 months after the end of treatment with romosozumab/placebo.

The pregnancy should be reported to Amgen Global Patient Safety within 24 hours of the investigator's knowledge of the event of a pregnancy. Report a pregnancy on the Pregnancy Notification Worksheet ([Appendix C](#)).

If a lactation case occurs while the subject is taking protocol-required therapies report the lactation case to Amgen as specified below.

Any lactation case should be reported to Amgen Global Patient Safety within 24 hours of the investigator's knowledge of event. Report a lactation case on the Lactation Notification Worksheet ([Appendix C](#)).

10. STATISTICAL CONSIDERATIONS

10.1 Study Endpoints, Analysis Sets, and Covariates

10.1.1 Study Endpoints

10.1.1.1 Primary Endpoint

- Percent change from baseline in DXA BMD at the lumbar spine at month 6

10.1.1.2 Secondary Endpoint

- Percent change from baseline in DXA BMD at the femoral neck and total hip at month 6

10.1.1.3 Exploratory Endpoints

- Percent changes from baseline in BTMs: P1NP and CTX at months 1, 3, and 6

10.1.1.4 Safety Endpoints

For the 6-month treatment period:

- Subject incidence of adverse events by system organ class and preferred term
- Changes from baseline in laboratory assessments (serum chemistry and hematology) and shifts from baseline to the worst value between baseline and month 6
- Changes from baseline in vital signs
- Incidence of subjects with anti-romosozumab antibodies at months 1, 3, and 6

For the overall study period (6-month treatment period followed by the 3-month follow-up period):

- Subject incidence of adverse events by system organ class and preferred term
- Subject incidence of the formation of anti-romosozumab antibodies

10.1.1.5 Pharmacokinetic Endpoint

- Romosozumab serum concentration at months 1, 3, and 6

10.1.2 Analysis Sets

The full analysis set includes all randomized subjects. Subjects in this set will be analyzed according to their randomized treatment assignment, regardless of treatment received.

The BMD efficacy analysis set for each BMD endpoint will include all randomized subjects who have a baseline DXA BMD measurement and at least 1 postbaseline DXA BMD measurement for the skeletal site (lumbar spine, femoral neck, or total hip) being evaluated. Data from subjects in this set will be analyzed according to randomized treatment groups, regardless of actual treatment received.

The BTM efficacy analysis set will include all randomized subjects who have a baseline measurement and at least 1 postbaseline measurement for the endpoint of interest (CTX, P1NP). Data from subjects in this set will be analyzed according to randomized treatment groups, regardless of actual treatment received.

The safety analysis set will include all randomized subjects who receive at least 1 dose of IP. These subjects will be analyzed according to their actual treatment received.

The pharmacokinetic set will include all subjects in the safety set who have evaluable serum romosozumab concentration. This set will be used in all PK analyses.

10.1.3 Covariates and Subgroups

All analyses assessing BMD endpoints at the lumbar spine, femoral neck, and total hip will include treatment group, baseline value of BMD, machine type and interaction of baseline BMD value, and machine type as independent covariates.

No subgroup analysis is planned.

10.2 Sample Size Considerations

The sample size is based on comparison of romosozumab to placebo on percent change in lumbar spine BMD at month 6. From earlier Study 20060326, the estimated mean percentage differences in lumbar spine BMD between romosozumab versus placebo at month 6 were 7.9 with 95% CI (6.6, 9.3). The standard deviations (romosozumab vs. placebo) of mean percentage change in lumbar spine BMD at month 6 were 3.9 vs. 3.8. A sample size of 30 subjects per treatment arm will provide >99% power to detect significant treatment difference (romosozumab vs. placebo) in percent change in lumbar spine BMD at month 6 assuming a mean percent difference of 6.6 and a standard deviation of 3.9 with two-sided type 1 error of 5% and 10% dropout rate under the two sample t-test.

10.3 Access to Individual Subject Treatment Assignments by Amgen or Designees

Blinded individuals will not have access to unblinded information until the study is formally unblinded. Unblinding and potentially unblinding information should not be distributed to the study team, investigators, or subjects prior to the study being formally unblinded (eg, the formal unblinding at the final analysis) except as specified (eg, [Section 5.2](#) and [Section 9.2.2.2](#)).

In order to perform limited planned analyses (eg, exposure-response analyses, PK analyses) or other key evaluations, certain functions may be unblinded to individual treatment assignments prior to the formal unblinding of the study. If such analyses will be performed during the conduct of the study, consider listing the functions and when they will become unblinded (eg, study milestone, percentage of study data availability).

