3. EXPERIMENTAL PLAN

3.1 Study Design

This is a multicenter, randomized, double-blind, placebo-controlled study in approximately 60 South Korean postmenopausal women with osteoporosis. The study is designed to evaluate if treatment with romosozumab QM for 6 months compared with placebo is effective in increasing BMD at the lumbar spine. In addition, the study will assess the effect of treatment with romosozumab QM for 6 months compared with placebo on BMD at the femoral neck and total hip.

Approximately 60 subjects will be randomized in a 1:1 ratio to receive 210 mg romosozumab subcutaneous (SC) QM (approximately 30 subjects) or matched placebo SC QM (approximately 30 subjects), respectively, in a blinded fashion for the duration of the 6-month treatment period.

Upon completion of the 6-month treatment period, subjects will be followed for an additional 3 months to ensure appropriate follow-up for anti-romosozumab antibody formation.

The overall study design is described by a [study schema](#) at the end of the protocol synopsis section.

From screening to end of study (EOS), subjects will receive daily calcium and vitamin D supplementation, which at a minimum should be in the range of 500 to 1000 mg elemental calcium and 600 to 800 IU vitamin D. In addition, subjects with a serum 25 (OH) vitamin D level of ≥ 20 ng/mL and ≤ 40 ng/mL at screening will receive an initial loading dose of 50 000 to 60 000 IU vitamin D after randomization (administered within 1 week of the study day 1 visit), preferably by the oral route. Subjects with a serum 25 (OH) vitamin D level of > 40 ng/mL at screening may also receive the vitamin D loading dose at the principal investigator's discretion.

The study endpoints are defined in [Section 10.1.1](#).

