10.4.2 Primary Analysis

The primary analysis will be performed after all subjects have had the opportunity to complete the month 6 visit.

The primary objective of the primary analysis is to evaluate the effect of treatment with romosozumab for 6 months compared with placebo on percent changes in BMD at the lumbar spine as assessed by DXA in South Korean women with osteoporosis. Formal statistical testing will be conducted to evaluate the following hypothesis: in South Korean women with osteoporosis, the mean percent change in lumbar spine BMD in subjects receiving romosozumab will be different to that of those receiving placebo at month 6.

Secondary objectives of the primary analysis include the evaluation of the effect of treatment with romosozumab compared with placebo on the following:

- Percent change from baseline in DXA BMD at the femoral neck and total hip at month 6

Exploratory objectives of the primary analysis include the evaluation of the effect of treatment with romosozumab for 6 months compared with placebo on the following:

- Percent changes from baseline in BTMs P1NP and CTX

For the exploratory objectives, all inferential statistics will be considered exploratory in nature.

Safety objectives of the primary analysis include the comparison of the safety and tolerability for 6-month treatment with 210 mg romosozumab QM to placebo in South Korean women with osteoporosis on the following:

- Subject incidence of adverse events, including Event of Interest (EOI)
- Changes from baseline in laboratory assessments (serum chemistry and hematology) and shifts from baseline to the worst value
- Changes from baseline in vital signs
- Incidence of subjects with anti-romosozumab antibodies

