10.4.3 Final Analysis

The final analysis will be performed after all subjects have had the opportunity to complete the month 9 visit (ie, after all subjects have had the opportunity to complete the 3-month follow-up **study** period). The 3-month follow-up period will provide the

opportunity to monitor all subjects for adverse events and formation of anti-romosozumab antibodies.

Final analysis will include the analysis of primary, secondary, exploratory efficacy endpoints, as well as the safety endpoints through 6-month treatment period and the analysis of safety endpoints (adverse events and formation of anti-romosozumab antibodies) for the 9-month study period.

The primary objective of the **final analysis** is the safety objective (ie, the comparison of the safety and tolerability following **9-month** treatment with 210 mg romosozumab QM to placebo in **South Korean** women with osteoporosis).

In the final analysis, data from the overall 9-month study period (6-month treatment period plus 3-month follow-up period) will be analyzed.

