Infant date of birth: mm ____ / dd ____ / yyyy ____

Infant gender: Female Male

Is the infant healthy? Yes No Unknown N/A

If any Adverse Event was experienced by the mother or the infant, provide brief details: _____

Form Completed by:

Print Name: _____ Title: _____

Signature: _____ Date: _____

Amendment 2

Protocol Title: A Multicenter, Randomized, Double-blind, Placebo-controlled, Study to Compare the Efficacy and Safety of Romosozumab With Placebo in Postmenopausal South Korean Women With Osteoporosis

Amgen Protocol Number Romosozumab (AMG 785) 20150242

Amendment Date: 13 November 2017

Rationale:

This study is being conducted to support registration of romosozumab in Korea.

A primary analysis at 6 months is being added in this protocol amendment. Conducting a primary analysis in addition to a final analysis allows evaluation of the efficacy and safety data in the most expedited manner to support registrational activities.

Importantly, the primary analysis is being added to maintain consistency with what was done in previous studies with a similar design in the romosozumab development program.

Additional updates include:

- Align End of Study and Publication Policy language to new template text
- Update schema to include primary and final analysis, and add month 5 visit to align with protocol
- Clarify adverse events of interest to include injection site reactions and potential events of serious cardiovascular adverse events
- Make editorial and administrative edits

Description of Changes:

[Section: Global](#)

Change: Date updated throughout from 09 June 2017 to **13 November 2017**.

[figure not shown]
[Section: Title Page](#)

Add:

[figure not shown]
Amendment 02 Date 13 November 2017

[Section: Study Design and Treatment Schema](#)

Replace:

With:

Section: Study Glossary

Add:

EOI	Event of Interest
------------	--------------------------

Section: 3.5.2 End of Study paragraph 1

Add:

The primary completion date is defined as the date when the last subject is assessed or receives an intervention for the final collection of data for the primary endpoint(s), for the purpose of conducting the primary analysis, whether the study concluded as planned in the protocol or was terminated early.

Section: 3.5.2 End of Study paragraph 4

Add:

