7.5 Pharmacokinetic Set

The pharmacokinetic set includes all subjects in the safety set who have evaluable serum romosozumab concentration. This set will be used in all PK analyses.

8. Interim Analysis and Early Stopping Guidelines

No interim analysis is planned for this study.

The primary analysis will occur after all subjects have had the opportunity to complete the Month 6 study visit. The final analysis will be performed after all subjects have had the opportunity to complete the Month 9 end of study visit.

9. Data Screening and Acceptance

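### Does adding a Month 6 primary analysis leave the blind unprotected between Month 6 and Month 9?

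*Protocol*

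**What the plan says.** The rationale for Amendment 2 explains the extra analysis: "Conducting a primary analysis in addition to a final analysis allows evaluation of the efficacy and safety data in the most expedited manner". Protocol 10.4.2 places it after every subject could have attended Month 6 and makes it confirmatory: "Formal statistical testing will be conducted to evaluate the following hypothesis". SAP Section 8 gives the same timing: "The primary analysis will occur after all subjects have had the opportunity to complete the Month 6 study visit". Adverse events and antibodies are still collected to Month 9, and Protocol 10.4.3 puts the final analysis after that visit.

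Protocol 10.3 governs access to treatment codes, in three steps:

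- Unblinding information is kept from the study team, investigators and subjects "prior to the study being formally unblinded (eg, the formal unblinding at the final analysis"), apart from the exceptions it cross-refers to.
- For limited planned analyses or other key evaluations, "certain functions may be unblinded to individual treatment assignments prior to the formal unblinding of the study".
- If that happens during the study, the text says to "consider listing the functions and when they will become unblinded". No list follows.

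Protocol 3.1 and SAP 3.1 say product is given "in a blinded fashion for the duration of the 6-month treatment period". Protocol 10.4.3 words the main objective of the final analysis as comparing "safety and tolerability following 9-month treatment with 210 mg romosozumab QM to placebo in" South Korean women with osteoporosis.

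**The concern.** A between-arm test at Month 6 requires someone to hold treatment codes while some women may still be in follow-up. Section 10.3 does not name those people, never mentions Month 6 or the primary analysis, and gives the final analysis only as an example of formal unblinding. The sentence about listing functions is plainly leftover template text, and Amendment 2's list of changes shows no edit to 10.3. The SAP text available gives the timing of both analyses but no unblinding rule.

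At stake would be the safety record for Months 6 to 9. Adverse events over the whole 9 months are a stated endpoint (Protocol 10.1.1.4), and investigators judge relatedness (9.2.2.1). If arm-level results or individual codes reached the sites early, those judgments could be coloured. The mention of 9 months of treatment in 10.4.3 adds to the impression that the section was not fully reconciled when it was amended.

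**Working it through.** **1. The plan's own figure.** Protocol 10.2 and SAP 3.2 give a difference of 6.6, SD 3.9, two-sided alpha 0.05, 30 per arm, 10% dropout and power above 99%. After dropout, n = 30 × 0.9 = 27 per arm. The noncentrality is 6.6 / (3.9 × √(2/27)) = 6.22, and the two-sample t-test power is about 0.99998. With n = 30 it is 6.6 / (3.9 × √(2/30)) = 6.55, and power is about 0.999996. The stated figure is reproduced. Nothing in it depends on who is unblinded after Month 6.

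**2. Can the gap reach the primary result?** Table 1 of the protocol schedules DXA at screening and Month 6 only. Scans are read by the central imaging vendor (7.3.13), and the primary analysis waits until all subjects could have attended Month 6. So scheduled primary and secondary endpoint data are collected before anyone needs the codes. The final analysis repeats the efficacy analyses, but on the same Month 6 endpoints, and SAP 9.4 states that no valid measurement will be purposely excluded.

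**3. What protects Months 6 to 9?**

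| Protocol section | Control | Ends at Month 6? |
|---|---|---|
| 5.2 | Site unblinding only when essential to managing the subject; otherwise a deviation | No end date |
| 7.3.12 | PK results withheld | No end date |
| 7.3.13.2 | Post-screening BMD withheld, including from sites | No end date |
| 7.4 | Marker, calcium and antibody results withheld after day 1, with stated exceptions | No end date |
| 10.3 | Study team, investigators and subjects kept blind until formal unblinding | Example given is the final analysis, after Month 9 |

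None of these lapses because an analysis is run at Month 6.

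**4. Does 3.1 end the blind at Month 6?** No. The sentence describes how subjects receive product. Dosing visits run from day 1 to month 5 (6.2.1.1), so the sentence is about administration and is silent on when codes are released.

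**5. Is the Month 6 analysis workable under 10.3?** Yes. The allowance for certain functions, read with the reference to key evaluations, covers a separate unblinded group. Running the analysis does not of itself give investigators individual codes.

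**6. How many women could be affected?** The documents give neither the enrolment length E nor the lag L from the last Month 6 visit to results, so both must be assumed. With even enrolment of 60, the number still in follow-up is 60 × min(1, (3 − L)/E), and zero once L reaches 3 months:

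- E = 3, L = 0: 60 × 3/3 = 60
- E = 6, L = 1: 60 × 2/6 = 20
- E = 12, L = 2: 60 × 1/12 = 5
- any E, L = 3: 0

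The answer runs from everyone to no one, and it counts women, not bias.

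**7. The 10.4.3 wording.** The phrase refers to 9 months of treatment. The last sentence of the same section divides 9 months into 6 of treatment and 3 of follow-up. Protocol 3.5.1 gives the same split, 6.2.1.1 lists six dosing visits, and 10.5.5.1 describes Months 6 to 9 as untreated. The passages conflict and are to be reconciled editorially. The safety periods actually analysed are defined in 10.1.1.4, 10.5.5.1 and SAP 10.7.1, and none of them uses the phrase.

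**The case for a change.** The best case for a change is that a registration trial should leave a written record of who was unblinded and when. Data cleaning and protocol-deviation review continue to database lock (SAP 9.4 and 10.3), investigators go on judging relatedness, and an example introduced by eg is not a commitment. Protocol 7.3.13.2 and 7.4 withhold exactly the data the Month 6 analysis needs, so the text might be expected to say who receives them. The remedy would be a few sentences and would need no data or patients.

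Much of this stands as fact: the functions are not named, the template sentence is unfinished, and continuation of the blind to Month 9 is implied but not stated outright. What does not follow is a consequence. The allowance in 10.3 settles access for an analysis group, and the controls on everyone else have no Month 6 end date. Safety has no inferential testing (Protocol 10.5.5).

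The status of the adjudicators cannot be settled here. The bar in 10.3 does not name them, and the adjudication charter cited in 7.3.11 is not among the documents. It is therefore not evidence of a lapse.

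**Conclusion.** No change to the plan follows. Followed as written, it gives a sound primary result and sound descriptive safety summaries. The unnamed functions are a gap that a sponsor's analysts fill sensibly with a separate unblinded group, and the natural reading of 10.3 keeps the study team, investigators and subjects blind until the final analysis. The leftover instruction in 10.3 is a drafting slip. The treatment-length phrase in 10.4.3 is a wording conflict, answered by the sentence after it, that no analysis depends on.

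The size is nil for alpha, power and the primary estimate. For Months 6 to 9 no bias is shown, and the number of women still in follow-up when results exist cannot be fixed from the documents (0 to 60 under the assumed enrolment and lag). The conclusion rests on two assumptions: that the Month 6 analysis counts as one of the evaluations for which 10.3 allows early access, and that the removed SAP front matter and redacted text contain nothing to the contrary.
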